6.3. Risks to Confidentiality

Patients will grant the experimenters access to protected health information. They will also reveal sensitive information about themselves, which will include their psychiatric status and any history of substance abuse. Subjects may feel uncomfortable revealing this information, and there is a risk of losing confidentiality. Subjects will also be informed in the consent document that confidentiality will be limited in cases where the subject reveals intentions to harm themselves or others, and the investigator feels that the proper authorities may need to be notified in order to prevent the occurrence of harm to the subject, or others.

Subject confidentiality is strictly held in trust by the participating investigators, their staff, and the sponsor(s) and their agents. The study protocol, documentation, data, and all other information generated will be held in strict confidence. All files will be kept secure and only authorized research personnel will have access. Only staff members who have a need to know personal identifying information will have access to this information.

All subject data will be kept strictly confidential, and no subject-identifying information will be released to anyone outside the project. Confidentiality will be through several mechanisms. First, each subject will be assigned a unique subject number which will then be used on all study forms, including the electronic data capture system (EDC). Secondly, any study forms, blood samples, or paper records that contain subject information will be

kept at the clinical sites in secured areas, and identified by the unique subject number. Once blood is collected, there will be no subject identifiers placed on blood samples, only the unique subject number and the date of sample collection. Third, access to all subject data and information, including laboratory specimens, will be restricted to authorized personnel. In the case of computerized data, this restricted access will be assured through user logon IDs and password protection. This protects forms from unauthorized view and modifications as well as inadvertent loss or damage.

Any data, forms, reports, and other records that leave the site will not contain the subject's name or any other direct identifier. The subject will be identified by a unique identifier to maintain subject confidentiality. Information will not be released without written permission of the participant, except as necessary for monitoring by the Institutional Review Board (IRB), the NIMH DSMB, the FDA, the government Office of Human Research Protections (OHRP) and/or any other government officials, safety monitors/committees that may need the information to make sure that the study is done in a safe and proper manner, learn more about side effects, and/or analyze the results of the study.

All subject data will be kept strictly confidential, and no subject-identifying information will be released to anyone outside the project. Confidentiality will be through several mechanisms. First, each subject will be assigned an anonymous study unique subject number which will then be used on all study forms, including the electronic data capture system (EDC). Secondly, any study forms, blood samples, or paper records that contain subject information will be kept at the clinical sites in secured, locked areas, and identified by the coded by unique subject number. Once blood is collected, there will be no subject identifiers placed on blood samples, only the unique subject number and the date of sample collection. Third, access to all subject data and information, including laboratory specimens, will be restricted to authorized personnel. In the case of computerized data, this restricted access will be assured through user logon IDs and password protection. This protects forms from unauthorized view and modifications as well as inadvertent loss or damage.

6.4. Risks Associated with Treatment

The most important risk identified in studies carried out to date is a potential risk of worsening of peptic ulcer disease in patients with gastric infection with Helicobacter pylori. This is based on findings of decreased parietal cells and inflammation in the stomach of rats.

In addition, subjects with a history of peptic ulcer disease or gastritis will also be excluded from participating in the study.

Other risks associated with the study drug include: headache, diarrhea, nausea, vomiting, flushing, anxiety, upset stomach, itchiness, and ventricular tachycardia (rapid heartbeat that requires immediate medical attention which was observed in 1 subject in the prior

studies). There is also the possibility that CERC-501 might lead to symptoms of depression based on the fact that this agent might have some mu opioid antagonist effects which several lines of evidence suggest might be depressogenic (Berrocoso et al., 2009; Escriba et al., 2004; Kennedy et al., 2006).

In addition to these risks there may be other risks of the study medication which are currently unknown as the number of individuals treated with this medication so far is limited.

To protect subjects from such unknown risks we will not allow subjects to participate in the study if they have: 1) any clinically significant abnormality on the screening tests; 2) any clinically significant medical, psychiatric, or substance use-related disorder other than a mood and anxiety spectrum disorder. ; 3) excessive alcohol intake or unwillingness to stop alcohol consumption for the duration of the study; 4) taken a prescribed medication within 30 days of the first study day, or nonprescription medication except vitamins and acetaminophen (up to 4 g/day) within 15 days of starting study drug, or need to continue any medication during the study; 5) taken an investigational medication within 3 months prior to the start of this study; 6) smoked cigarettes within the last month or at any time during the study; or 7) a history of severe allergies or multiple adverse drug reactions.

We will further protect subjects from unanticipated risks by monitoring for adverse effects at every visit during treatment by carefully checking for any adverse reactions and by assessing suicidality with the Columbia Suicide Severity Rating Scale (CSSRS) and the CGI-S. If subjects experience an adverse reaction, appropriate medical care will be provided. This may include referral to an appropriate practitioner outside of the study, transfer to an Emergency Room, or hospital admission. Subjects will be monitored regularly until the adverse reaction is resolved. Unexpected adverse reactions occurring during the period of participation in the study or that are relevant to subjects after their participation in the study will be communicated to them. All adverse reactions will be reviewed by the NIMH Data and Safety Monitoring Board. They will make ongoing evaluations of the risks of study participation and can recommend that the study be terminated in cases where the risks are deemed to be excessive.

6.5. Risks of Venipuncture

Subjects will undergo venipuncture 6 times during the study. Complications of drawing blood from a vein occur approximately 2% of the time and include discomfort at the site of puncture; possible bruising and swelling around the puncture site; rarely an infection; and, uncommonly, faintness from the procedure.

In order to minimize the risks of drawing blood from a vein, sterile technique will always be used and these procedures will be carried out by individuals with sufficient training.

6.6. Risks Associated with fMRI Scanning

The risks associated with fMRI scanning include the development of anxiety inside the scanner (occurs in 5-10%) and the possibility of injury due to movement of a magnetic

object in the scanner room. In order to reduce the risk of developing fear during MRI procedures, subjects will have a practice MRI scanning session before having any MRI scans to help them get used to being inside the MRI scanner. Rarely people develop anxiety inside the scanner and decide not to continue in the study. This session will provide subjects with an opportunity to make sure they are comfortable with proceeding with MRI scanning.

Risks of injury during MRI will be reduced by evaluating subjects for risk factors including having implanted metal devices. If such risk factors are identified subjects would not be allowed to participate in the study. In addition, the area around the MRI scanner is kept free of objects that could pose a risk to subjects.

6.7. Risks associated with EEG and ECG studies

Risks associated with EEG and ECG studies: The risks associated with undergoing EEG and ECG studies include skin irritation at the sites electrodes are applied/removed and the general inconvenience of having to set aside time to undergo such monitoring. The risk of skin irritation will be minimized by having highly experienced individuals attach the electrodes and using methods that decrease the likelihood of irritation.

6.8. Risks to Those of Reproductive Potential

6.8.1. Females

Being a part of this study while pregnant may expose the unborn child to significant risks, some of which may be currently unforeseeable. In order to protect subjects from this risk, pregnant women will be excluded from the study. For all women of childbearing potential, a blood pregnancy test will be done and it must be negative before subjects can continue in this study. If sexually active, subjects must agree to use appropriate contraceptive measures for the duration of the study and for 1 month afterwards. Medically acceptable contraceptives include: (1) surgical sterilization (such as a tubal ligation or hysterectomy), (2) approved hormonal contraceptives (such as birth control pills, patches, implants or injections), (3) barrier methods (such as a condom or diaphragm) used with a spermicide, or (4) an intrauterine device (IUD). Contraceptive measures such as Plan B (TM), sold for emergency use after unprotected sex, are not acceptable methods for routine use. If subjects do become pregnant during this study or if they have unprotected sex, they will be instructed to inform the study physician immediately.

6.8.2. Males

Participation in this research has the potential to damage sperm, which could cause harm to a child that a subject might father while on this study. Such harm may be currently unforeseeable. As a result, in order to protect subjects, sexually active male subjects will have to agree to use a medically acceptable form of birth control during and 1 month after this study in order to participate. Medically acceptable contraceptives include: (1) surgical sterilization (such as a vasectomy), or (2) a condom used with a spermicide. Contraceptive measures such as Plan B (TM), sold for emergency use after unprotected sex, are not acceptable methods for routine use. Subjects will be instructed to inform their
partners of the potential for harm to an unborn child and that they should immediately inform the study doctor if pregnancy occurs.

6.8.3. Pregnancy

This protocol does not allow for currently pregnant women to be included in the study, due to the unknown risk to the fetus with this medication. At study entry, all women must have a negative pregnancy test to be allowed to enroll into the study, and must practice an acceptable method of birth control while in the study. BHCG serum pregnancy tests will be performed for all women, unless surgically sterile, at the screening visit and if clinically indicated at any time during the study. All women of childbearing potential will be instructed to notify the Investigator if they become pregnant at any time during the study or within 30 days of last study evaluation. The pregnancy will be followed until delivery. If any subject is found to be pregnant during the study, study drug will be immediately discontinued. The subject will remain in the study for continued follow up of the pregnancy. If the pregnancy occurs in a female subject or the partner of a male subject during the study or within 30 days of the end of the study the investigator will inform the subject of their right to receive treatment information. If the female subject or partner agrees to the primary care physician being informed, the investigator will notify the primary care physician that the subject or her partner was participating in a clinical study at the time she became pregnant and provide details of treatment the subject received. All reported pregnancies will be followed up to final outcome. The outcome, including any premature termination, will be reported on the appropriate CRF page.

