4.3. Screening

Screening Visit: Day -30 to Day -1 (4 - 6 hours)

Once a subject has signed an inform consent for this study subjects will undergo a set of screening tests to determine if they meet the inclusion/exclusion criteria for the study. These screening tests will include:

- Medical, psychiatric, and medication history
- Vital signs (temperature, blood pressure, and pulse)
- Physical examination
- Pregnancy Test (beta-HCG serum pregnancy test females only)
- Electrocardiogram (ECG)
- Urine drug screen
- Mini-International Neuropsychiatric Interview (MINI)
- Snaith-Hamilton Pleasure Scale (SHAPS)
- Temporal Experience of Pleasure Scale (TEPS)
- Visual Analogue Scale for Anhedonia (VAS)
- Columbia Suicide Severity Rating Scale (CSSRS)
- Clinical Global Impression Severity (CGI-S)
- Battery of clinical laboratory tests including: Complete blood count with differential, Electrolytes, Metabolic Panel, Thyroid Function Tests, Urinalysis
- Mock MRI scanning session

Those who qualify to continue with the study based on the screening assessment will be asked to return 1-30 days later for additional evaluations. Subjects who require medication tapering will discuss a medication tapering plan with a study physician during

this visit (for details see Section 4.1. Study Overview). This plan will be designed so that subjects are free of all excluded medications at least 5 half-lives prior to the baseline visit (see Section 3.3. Exclusion Criteria). Qualifying subjects will be instructed about not using any prohibited medications during the study including substances of abuse. They will be specifically instructed about not using Salvia divinorum, which has kappa opioid agonist effects and is not an illegal substance.

A potential subject who previously screen failed due to a positive breath test ONLY may be brought back for re-screening. Subject should sign a new informed consent and all screening procedures must be repeated.

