4.4. Study Procedures

Baseline: Day 0 Visit (6 – 8 hours):

Following rigorous screening, subjects will return to the clinic/research unit up to 30 days later and undergo the following assessments and procedures:

- Structural MRI, fMRI during Monetary Incentive Delay Task, Resting State Connectivity fMRI
- Interval history
- Battery of clinical laboratory tests including: Complete blood count with differential, Electrolytes, Metabolic Panel, Thyroid Function Tests, Urinalysis.
- EEG
- Vital signs (temperature, blood pressure, and pulse)
- Physical examination
- Electrocardiogram (ECG)
- Snaith-Hamilton Pleasure Scale (SHAPS)
- Temporal Experience of Pleasure Scale (TEPS)
- Visual Analogue Scale for Anhedonia (VAS)
- Columbia Suicide Severity Rating Scale (CSSRS)
- Probabilistic Rewards Task (PRT)
- Effort Expenditure for Rewards Task (EEfRT)
- Hamilton Depression Rating Scale (HAM-D)
- Hamilton Anxiety Rating Scale (HAM-A)
- The Cognitive and Physical Functioning Questionnaire (CPFQ)
- Clinical Global Impression Severity (CGI-S)
- Clinical Global Impression Improvement (CGI-I)
- Adverse events assessment with the Patient Reported Inventory of Side-Effects (PRISE)
- Blood sample collection for tests for assessment for gastric adverse events including gastrin, and pepsinogen I/II levels.
- Blood sample collection to be sent to Rutgers for potential genetic analysis or other future analysis (optional)

At the end of this visit subjects will be randomized to CERC-501 10 mg or placebo, will be provided with enough study medication for a 2-week period and will be instructed to take the medication every morning. Subjects will also be instructed to bring all of their study drug packaging and unused study drug with them to each visit.

Week 1 – Telephone Follow Up:

Subjects will be called after one week to assess for any safety concerns. Any safety issues identified will be addressed as appropriate.

Week 2 Visits (4 – 6 hours per visit): +/- 4 days

At this visit subjects will undergo the following assessments and procedures:

- Interval history
- Battery of clinical laboratory tests including: Complete blood count with differential, Electrolytes, Metabolic Panel, Thyroid Function Tests, Urinalysis
- Vital signs (temperature, blood pressure, and pulse)
- Physical examination
- Electrocardiogram (ECG)
- Snaith-Hamilton Pleasure Scale (SHAPS)
- Temporal Experience of Pleasure Scale (TEPS)
- Visual Analogue Scale for Anhedonia (VAS)

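### The only scheduled pregnancy test is at Screening, 1 to 30 days before dispensing, so no pregnancy result is required between Screening and the first dose

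*Protocol*

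**What the plan says.** Protocol Section 6.8.3 fixes the timing: "BHCG serum pregnancy tests will be performed for all women, unless surgically sterile, at the screening visit and if clinically indicated". The rest of that sentence lets a clinically indicated test be done at any point in the trial. The same section sets the entry condition, "At study entry, all women must have a negative pregnancy test to be allowed to enroll into the study", and gives the reason for excluding pregnant women: "due to the unknown risk to the fetus with this medication". If pregnancy is discovered later, "If any subject is found to be pregnant during the study, study drug will be immediately discontinued".

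The schedule agrees with this. Table 3 marks serum HCG once, in the Screening column. Section 4.3 lists the test among the Screening procedures, and the SAP Study Flow Chart names a pregnancy test under Screening and at no other visit.

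On the interval, Section 4.3 says: "Those who qualify to continue with the study based on the screening assessment will be asked to return 1-30 days later". At the end of the Baseline visit in Section 4.4, subjects are randomised and "will be provided with enough study medication for a 2-week period and will be instructed to take the medication every morning". The laboratory work at that visit is itemised as "Battery of clinical laboratory tests including: Complete blood count with differential, Electrolytes, Metabolic Panel, Thyroid Function Tests, Urinalysis", with no HCG.

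**The concern.** Pregnancy or lactation is exclusion 18. Section 6.8.1 warns of significant risk to the unborn child, some of it perhaps not yet foreseeable. The exclusion matters most when drug is handed over, yet the only required evidence may be 30 days old by then. A woman who conceives after Screening without knowing it could be randomised and sent home with two weeks of drug.

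For some subjects the interval cannot be kept short. Sections 4.1 and 4.3 have those on excluded medication agree a taper at Screening and be clear of it for at least 5 half-lives before Baseline.

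What is at stake is fetal exposure to an investigational drug, not the validity of the comparison between arms.

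**Working it through.** The plan states no figure to reproduce, so the check sets every mention of pregnancy testing beside the visit schedule and then counts.

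**Where a test is placed**

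| Source | Timing given |
|---|---|
| Protocol Table 3 | Screening only |
| Protocol 4.1 (screening assessments) and 4.3 | Screening |
| Protocol 6.8.3 | Screening, otherwise when clinically indicated |
| SAP Study Flow Chart | Screening |
| Protocol 4.1 (Baseline) and 4.4 (Baseline, Weeks 2 to 8, Week 12) | No test listed |
| Protocol 7.1 and 16.1 | HCG named as a safety assessment, no visit given |
| Protocol 6.8.1 and 10.1.4 | Negative blood test before continuing, no date and no maximum age of result |

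Sections 7.1 and 16.1 do not create a Baseline test. They are general lists of assessments, and Table 3 is what assigns assessments to visits. The entry conditions in 6.8.1, 6.8.3 and 10.1.4 do not create one either, because a negative Screening result of any age within the window satisfies them.

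**Counts**

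- Contacts in Table 3: Screening, A0, the Week 1 call, A1, A2, A3, A4 and the 1-month follow-up, 8 in all. HCG is scheduled at 1. The general laboratory battery is scheduled at 6 (Screening, A0, A1 to A4).
- Age of the only scheduled result at A0: 1 to 30 days (Section 4.3).
- Doses dispensed at A0: 2 weeks × 7 = 14. Planned total: 8 weeks × 7 = 56.
- Women expected: Section 4.2 anticipates twice as many women as men, so 90 × 2/3 = 60. At 1:1 allocation, 60 / 2 = 30 would receive CERC-501.
- If the sex ratio differs: 90 × 0.5 = 45 women if half are women, and 90 at the limit if all are.

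**What a test at A0 would add.** It moves the latest detectable conception forward by at most the Screening-to-A0 interval of 1 to 30 days, and by less if the urine test turns positive later after conception than serum does. The documents give no assay figures, so that difference is left unquantified. They give no conception rate and no number of women of childbearing potential either, so no expected number of pregnancies is calculated.

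**The case against.** The strongest reply is that the plan already has several layers of protection.

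- Section 4.1 randomises only subjects who still qualify at the end of Baseline, so exclusion 18 is meant to hold then.
- Site staff take an interval history and do a physical examination at A0, and may order a serum test if they see reason to.
- Inclusion 7 requires women of childbearing potential to agree to dual contraception. Oral contraception must have begun at least 2 months before Baseline, which spans the whole Screening interval.
- Women are told to report pregnancy or unprotected sex at once (Section 6.8.1), a safety call is made at Week 1, and drug stops if pregnancy is found.
- Section 1.2.3.5 reports that reproductive and genotoxicity studies were done, that the drug was not genotoxic, and that the nonclinical profile was judged acceptable for this study.

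All of this stands, and it makes a case unlikely. None of it detects a pregnancy that nobody suspects. The eligibility check has no new pregnancy result to draw on, the permitted test needs a prompt, and contraception lowers the probability without verifying the outcome. The protocol itself requires a test as well as contraception. The nonclinical summary does not displace Section 6.8.3, which still calls the fetal risk unknown.

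It is also fair to say that a test at A0 leaves the 8 weeks of dosing without a scheduled test. That limits what the fix achieves but does not argue against making it.

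Three stronger readings are tempting, and the documents support none of them:

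- **The protocol contradicts itself by requiring a negative test at study entry.** It does not: a Screening result meets that condition as written.
- **Pregnancies should be expected in this trial.** No document gives a conception rate, and many of the 60 women may not be at risk, since eligibility runs to age 65.
- **The gap could bias the result.** The schedule is the same in both arms and the gap precedes randomisation.

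**Conclusion.** The gap is real and is one of subject safety. Serum HCG is scheduled at 1 of 8 contacts, and the result is 1 to 30 days old when 14 of 56 doses are dispensed. Nothing in either document requires a newer result. An unrecognised conception after Screening would not be found before dosing.

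The likelihood is low, and the case rests on the possible consequence and the very small cost of prevention, not on frequency. The schedule facts need no assumption. The figure of about 60 women rests on the anticipated 2:1 ratio and is an expectation, not a maximum.

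**What to change.** On arrival at A0, before the scan and randomisation, run a rapid urine pregnancy test for every woman who is not surgically sterile. Use the urine already collected for urinalysis, taken at the start of the visit.

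- **Negative:** proceed.
- **Positive:** hold randomisation until serum HCG is back. A positive serum result is a screen failure. A negative one allows randomisation, with a short stated extension of the 30-day window where waiting would otherwise breach it.

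Add the test to the A0 column of Table 3, the Baseline list in Section 4.4 and Section 6.8.3.

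The cost is a short amendment and about 60 rapid tests if the 2:1 ratio holds (45 if half the subjects are women, 90 if all are). Leaving out surgically sterile women lowers the number, and subjects who fail at Baseline add a few. The downside is an occasional late screen failure, or a randomisation delayed by a false positive. The change does not cover conceptions very shortly before A0 or during treatment.
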